7.2.1.3 Hematologic response

A complete hematologic response (CHR) is defined as all of the following present for ≥ 4 weeks:

- WBC count $<10 \times 10^9/L$
- Platelet count $<450 \times 10^9/L$
- Basophils $<5\%$
- No blasts and promyelocytes in peripheral blood
- Myelocytes + metamyelocytes $< 5\%$ in peripheral blood
- No evidence of extramedullary disease, including spleen and liver

7.2.2 Safety and tolerability assessments

Safety will be monitored by the assessments described below as well as collecting of the adverse events at every visit. For details on AE collection and reporting, refer to [Section 8](#). Significant findings that were present prior to the signing of informed consent must be included in the Relevant Medical History/Current Medical Conditions page on the patient's eCRF. Significant new findings that begin or worsen after informed consent must be recorded on the AE page of the patient's eCRF.

7.2.2.1 Physical examination

A complete physical examination will include the examination of general appearance, skin, neck (including thyroid), eyes, ears, nose, throat, lungs, heart, abdomen, back, lymph nodes, extremities, vascular and neurological. Information about the physical examination must be present in the source documentation at the study center and will be collected on the following visits as specified in [Table 7-1](#) and [Table 7-2](#):

- Screening /S-Screening
- Week 1 Day 1 / S-Week 1 Day 1
- Every 2 weeks from Week 4 to Week 16 / S-Week 4 to S-Week 16. Week 6, 10 and 14 / S-Week 6, 10 and 14 assessments must be performed in case of previous or newly occurring adverse events.
- Every 4 weeks from Week 16 to Week 96 / S-Week 16 to S-Week 96
- Every 12 weeks from Week 96 to EOT / S-Week 96 to S-EOT
- End of treatment / S-End of treatment visit or early discontinuation / S-early discontinuation visit in case of premature discontinuation.

Significant findings that were present prior to the signing of informed consent must be included in the Medical History page on the patient's eCRF. Significant new findings that begin or worsen after informed consent must be recorded on the Adverse Event page of the patient's eCRF. Presence of extramedullary leukemic involvement will be checked with each physical examination as outlined above. Findings on physical examination consistent with extramedullary leukemic involvement will be recorded (e.g. liver and spleen size, any other organ involvement).

7.2.2.2 Vital signs

Vital signs include blood pressure (supine position preferred when ECG is collected), pulse measurement, and body temperature and must be performed at the following visits as specified in [Table 7-1](#) and [Table 7-2](#):

- Screening / S-Screening
- Week 1 Day 1 / S-Week 1 Day 1
- Week 2 Day 1 / S-Week 2 Day 1
- Every 2 weeks from Week 4 to Week 16 / S-Week 4 to S-Week 16
- Every 4 weeks from Week 16 to Week 96 / S-Week 16 to S-Week 96
- Every 12 weeks from Week 96 to EOT/ S-Week 96 to S-EOT
- End of treatment / S-End of treatment visit or early discontinuation / S-early discontinuation visit in case of premature discontinuation.

7.2.2.3 Height and weight

Height in centimeters (cm) will be measured at screening only.

Body weight (to the nearest 0.1 kilogram [kg] in indoor clothing, but without shoes) will be measured at screening and at subsequent time points as specified in [Table 7-1](#) and [Table 7-2](#):

- Screening / S-Screening

- Week 1 Day 1 / S-Week 1 Day 1
- Every 12 weeks from Week 12 to EOT / S-Week 12 to S-EOT
- End of treatment visit / S-End of treatment or early discontinuation / S-early discontinuation visit in case of premature discontinuation.

7.2.2.4 Performance status

ECOG Performance status scale (Table 7-4) will be used as described in the Table 7-1, Table 7-2 and Table 7-4:

- Screening / S-Screening
- Week 1 Day 1 / S-Week 1 Day 1
- Every 2 weeks from Week 4 to Week 16 / S-Week 4 to S-Week 16
- Every 4 weeks from Week 16 to Week 96 / S-Week 16 to S-Week 96
- Every 12 weeks from Week 96 to EOT / S-Week 96 to S-EOT
- End of treatment / S-End of treatment visit or early discontinuation / S-early discontinuation visit in case of premature discontinuation.

More frequent examinations may be performed at the investigator's discretion, if medically indicated.

Table 7-4 ECOG Performance status scale

Description	Grade
Fully active, able to carry on all pre-disease activities without restriction.	0
Restricted in physically strenuous activity but ambulatory and able to carry out work of a light or sedentary nature e.g. light housework, office work.	1
Ambulatory and capable of all self-care but unable to carry out any work activities. Up and about more than 50% of waking hours.	2
Capable of only limited self-care, confined to bed or chair more than 50% of waking hours.	3
Completely disabled. Cannot carry on any self-care. Totally confined to bed or chair.	4
Dead.	5

7.2.2.5 Laboratory evaluations

Central laboratory will be used for analysis of hematology, biochemistry, coagulation, serum pregnancy and hepatitis marker specimens collected (safety monitoring) as specified in Table 7-1, Table 7-2 and Table 7-5. Details on the collections, shipment of the samples and reporting of results by the central laboratory are provided to investigators in the [CABL001A2301 Laboratory Manual]. The time windows granted for laboratory evaluations are identical with the corresponding visit time windows for each visit (see Section 7.1.5).

Local laboratory analysis are allowed if there is a clinical suspicion of abnormal laboratory values which is supported by a reported adverse event and for hematology assessments at Week 6, 10 and 14.

[figure not shown]
[figure not shown]

Table 7-5 Central clinical laboratory parameters collection plan

Test Category	Test Name	Frequency
Hematology	Hemoglobin, platelets, red blood cells, white blood cells, WBC morphology with differential (basophils, eosinophils, lymphocytes, monocytes, neutrophils, promyelocytes, myelocytes, metamyelocytes, blast and other)	Screening/baseline, Week 1 Day 1, Week 2 Day 1, every 2 weeks from week 4 up to week 16, every 4 weeks up to week 96, and every 12 weeks thereafter, EOT and as clinically indicated / S-Screening/S-baseline*, S-Week 1 Day 1, S-Week 2 Day 1, every 2 weeks from S-week 4 up to S-week 16, every 4 weeks up to S-week 96, and every 12 weeks thereafter, S-EOT and as clinically indicated
Chemistry	Hemoglobin A1c	Screening/baseline, Week 12 and as clinically indicated / S-Screening/S-baseline*, S-Week 12 and as clinically indicated
Chemistry	Creatinine clearance	Screening/baseline / S-Screening/S-baseline*
Chemistry	Albumin, alkaline phosphatase, ALT (SGPT), AST (SGOT), total calcium, total calcium (corrected for albumin), creatinine, creatine kinase, potassium, magnesium, sodium, phosphate (inorganic phosphorus), direct bilirubin, indirect bilirubin, total bilirubin, total cholesterol, LDL cholesterol, HDL cholesterol, total protein, triglycerides, blood urea or Blood Urea Nitrogen (BUN), uric acid, amylase, lipase, glucose (fasting)	Screening/baseline, Week 1 Day 1, Week 2 Day 1, every 4 weeks from week 4 up to week 96, and every 12 weeks thereafter, EOT, and as clinically indicated / S-Screening/S-baseline*, S-Week 1 Day 1, S-Week 2 Day 1, every 4 weeks from S-week 4 up to S-week 96, and every 12 weeks thereafter, S-EOT, and as clinically indicated
Coagulation	International Normalized Ratio (INR)	
Hepatitis markers	HbsAg, HbcAb /anti-Hbc	Screening/baseline**
Serum Pregnancy test (if applicable)	Serum β -HCG testing	Screening/baseline, every 4 weeks up to week 96, and every 12 weeks thereafter, EOT, unscheduled / S-Screening/S-baseline*, every 4 weeks up to S-week 96, and every 12 weeks thereafter, S-EOT, unscheduled

*Assessment does not need to be completed during the screening visit for patients in the treatment switch if already collected during the EOT.
 
**Not applicable for patients being assessed for treatment switch as part of the treatment switch screening/baseline visit.
		

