4.1.1 Study treatment switch from bosutinib to asciminib

Patients with documented treatment failure (as per the 2013 ELN guidelines; [Baccarani et al 2013](#)) while on bosutinib treatment will have the option to switch to asciminib treatment within 96 weeks after the last patient has been randomized on study. The patients who switch to asciminib will be able to receive asciminib up to end of study treatment period. At the end of the treatment period for patients who, in the opinion of the investigator still derive clinical benefit, asciminib treatment will be made available through alternative options including, but not limited to, an expanded access/compassionate use/managed access program or access to commercial supplies in applicable countries. Discontinuation of asciminib for patients who have switched over from bosutinib must follow the guidelines provided in [Section 7.1.6](#). Eligibility criteria for patients switching to asciminib are described in [Section 7.1](#).

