 13. Impairment of gastrointestinal (GI) function or GI disease that may significantly alter the absorption of study drug (e.g. ulcerative disease, uncontrolled nausea, vomiting, diarrhea, malabsorption syndrome, small bowel resection, or gastric bypass surgery)
 - 14a. Treatment with medications that meet one of the following criteria and that cannot be discontinued at least one week prior to the start of treatment with study treatment
 - Moderate or strong inducers of CYP3A
 - Moderate or strong inhibitors of CYP3A
 15. Previous treatment with or known/ suspected hypersensitivity to asciminib or any of its excipients.
 16. Previous treatment with or known/ suspected hypersensitivity to bosutinib or any of its excipients.
 17. Participation in a prior investigational study within 30 days prior to randomization or within 5 half-lives of the investigational product, whichever is longer
 18. Pregnant or nursing (lactating) women
 - 19a. Women of child-bearing potential, defined as all women physiologically capable of becoming pregnant, unless they are using highly effective methods of contraception during dosing and for 3 days after last dose of asciminib and one month after last dose of bosutinib. Highly effective contraception methods include:

- Total abstinence (when this is in line with the preferred and usual lifestyle of the subject. Periodic abstinence (e.g., calendar, ovulation, symptothermal, post-ovulation methods) and withdrawal are not acceptable methods of contraception)
- Female sterilization (have had surgical bilateral oophorectomy (with or without hysterectomy) total hysterectomy or bilateral tubal ligation at least six weeks before taking study treatment). In case of oophorectomy alone, only when the reproductive status of the woman has been confirmed by follow up hormone level assessment
- Male sterilization (at least 6 months prior to screening). The vasectomized male partner should be the sole partner for that subject.
- Use of oral, injected or implanted hormonal methods of contraception or placement of an intrauterine device (IUD) or intrauterine system (IUS) or other forms of hormonal contraception that have comparable efficacy (failure rate <1%), for example hormone vaginal ring or transdermal hormone contraception.
- In case of use of oral contraception women should have been stable on the same pill for a minimum of 3 months before taking study treatment.

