				S-Week 1 Day 1	S-Week 2 Day 1	S-Week 4	S-Week 6	S-Week 8	S-Week 10	S-Week 12	S-Week 14	S-Week 16	S-Week 20	S-Week 24	S-Week 28	S-Week 32	S-Week 36	S-Week 40	S-Week 44	S-Week 48	S-Week 52	
IRT			EOT (Bosutinib) / S-Screening/ S-Baseline																			
Treatment Switch Eligibility checklist	D		X																			
Treatment switch criteria	D		X																			
Mutation status	D	7.1.2.4	X																			
Prior/concomitant medications	D	7.1.2.4	X	Continuous																		
Physical examination	S	7.2.2.1	X	X		X	If needed	X	If needed	X	If needed	X	X	X	X	X	X	X	X	X	X	X
Extramedullary Involvement	D	7.2.2.1	X	X		X	If needed	X	If needed	X	If needed	X	X	X	X	X	X	X	X	X	X	X
ECOG Performance status	D	7.2.2.4	X	X		X	If needed	X	If needed	X	If needed	X	X	X	X	X	X	X	X	X	X	X
Weight	D	7.2.2.3	X	X						X				X			X			X		
Vital signs	D	7.2.2.2	X	X	X	X	If needed	X	If needed	X	If needed	X	X	X	X	X	X	X	X	X	X	X
Laboratory assessments		7.2.2.5																				

[figure not shown]
Visit name	Category	Protocol Section 7	Switch Screening Phase	Treatment Switch Phase																	
				S-Week 1 Day 1	S-Week 2 Day 1	S-Week 4	S-Week 6	S-Week 8	S-Week 10	S-Week 12	S-Week 14	S-Week 16	S-Week 20	S-Week 24	S-Week 28	S-Week 32	S-Week 36	S-Week 40	S-Week 44	S-Week 48	S-Week 52
Hematology	D	7.2.2.5.1	X (if not done at EOT)	X	X	X	X	X	X	X	X	X	X	X	X	X	X	X	X	X	
Chemistry	D	7.2.2.5.2	X (if not done at EOT)	X	X	X		X		X		X	X	X	X	X	X	X	X	X	
Chemistry-Hemoglobin A1c	D	7.2.2.5.2	X (if not done at EOT)	Week 12 and as clinically indicated																	
Coagulation	D	7.2.2.5.2	X (if not done at EOT)	X	X	X		X		X		X	X	X	X	X	X	X	X	X	
Serum Pregnancy test (if applicable)	D	7.2.2.5.3	X (if not done at EOT)			X		X		X		X	X	X	X	X	X	X	X	X	
Liver assessments	D			as clinically indicated																	

Visit name	Category	Protocol Section 7	Switch Screening Phase	Treatment Switch Phase																	
				S-Week 1 Day 1	S-Week 2 Day 1	S-Week 4	S-Week 6	S-Week 8	S-Week 10	S-Week 12	S-Week 14	S-Week 16	S-Week 20	S-Week 24	S-Week 28	S-Week 32	S-Week 36	S-Week 40	S-Week 44	S-Week 48	S-Week 52
Efficacy assessments		7.2.1																			
Blood collection for BCR-ABL1 quantification by RQ-PCR	D	7.2.1.1	X			X		X		X		X		X				X			X
Exploratory BCR-ABL1 Mutation analysis by Sanger sequencing	D	7.2.1.1		X (if not done at EOT)																	
Exploratory BCR-ABL1 Mutation analysis by Sanger sequencing for patients with mutations at Week 1 Day 1	D	7.2.1.1								X				X				X			X

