7.1.2 Screening

Written informed consent must be obtained before any study specific medical procedures are performed. All screening/baseline assessments (with the exception of Bone Marrow Aspirates) should occur within 21 days before Week 1 Day 1.

The screening visit window for bone marrow assessments is 56 days prior to Week 1 Day 1. Should bone marrow assessments have been performed before the main informed consent is signed but within 56 days of Week 1 Day 1, no further bone marrow sampling will be required at screening. At end of treatment, a bone marrow exploratory aspirate and/or biopsy must be collected even if the screening/baseline bone marrow exploratory aspirate and/or biopsy samples were not collected. During the screening visit, inclusion and exclusion criteria will be assessed. Screening assessments to confirm eligibility must be performed prior to randomization. The results of the real time quantitative polymerase chain reaction (RQ-PCR) and the bone marrow aspirate must be available prior to randomization and first dose of study treatment.

For details of assessments required during screening please refer to [Table 7-1](#).

Laboratory baseline assessments (including hematology, chemistry, coagulation and serum pregnancy test), physical examination including extramedullary involvement, performance status, ECG, height, weight and vital signs, evaluation of all relevant medical history including cardiovascular risk factors, CML disease history, including prior TKI therapy and antineoplastic medication and prior and concomitant medication must be performed prior to the first dose of study treatment. Patients with potassium, and/or magnesium and/or total calcium levels that are < LLN at screening, must have their potassium, and/or magnesium, and/or calcium replenished through supplementation and the levels must be within normal limits prior to the first dose of study drug.

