7.1.2.2 Conditions to be fulfilled for asciminib switch

The eligibility assessments of patients who are candidates for asciminib switch will start with the bosutinib EOT visit. Assessments conducted during the EOT visit will be used to evaluate if all conditions for asciminib switch are fulfilled and there are no conditions preventing patients from receiving asciminib treatment. Therefore all efforts **MUST** be made to ensure that all EOT assessments are completed per [Table 7-1](#). In the event that all EOT assessments cannot be completed during the EOT visit, they must be completed within 42 days (6 weeks) after the bosutinib EOT visit. For details of assessments required for patients that switch treatment from bosutinib to asciminib, please refer to [Table 7-2](#). The maximum allowed time frame for patients failing bosutinib to start treatment with asciminib is 42 days after bosutinib EOT.

In case a patient presents with a grade 3 or 4 adverse event at the time of the EOT visit or develops it after the EOT visit, the adverse event must be resolved to grade 2 or lower before starting asciminib treatment and within 28 days of the date of occurrence of the adverse event as outlined in the criteria listed below.

However, a patient who has laboratory test (peripheral blood test) results or ECG results that do not satisfy the treatment switch conditions may have the tests repeated multiple times during the treatment switch screening period. The last test performed before start of asciminib dosing must meet the conditions for treatment switch as listed below.

If a patient does not meet the conditions for treatment switch, they should enter the survival follow-up phase.

The conditions for treatment switch will be checked via the IRT system. Please refer and comply with detailed guidelines in the IRT manual.

Conditions to fulfill to allow the switch to asciminib:

1. Failure to bosutinib treatment up to 96 weeks after the last patient received the first dose (adapted from the 2013 ELN Guidelines; [Baccarani et al 2013](#)). Patients must meet at least 1 of the following criteria. Failure is defined as follows:
 - Three months after the initiation of therapy or thereafter: No CHR or > 95% Ph+ metaphases.
 - Six months after the initiation of therapy or thereafter: BCR-ABL1 ratio > 10% IS and/or > 65% Ph+ metaphases.
 - Twelve months after initiation of therapy or thereafter: BCR-ABL1 ratio > 10% IS and/or > 35% Ph+ metaphases.

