- At any time after the initiation of therapy, loss of CHR, CCyR or PCyR.
- At any time after the initiation of therapy, detection of new BCR-ABL1 mutations which potentially cause resistance to study treatment (asciminib or bosutinib).
- At any time after the initiation of therapy, confirmed loss of MMR in 2 consecutive tests.
- At any time after the initiation of therapy, new clonal chromosome abnormalities in Ph+ cells: CCA/Ph+.

Conditions preventing patients to switch to asciminib

- Any Grade 3 or 4 toxicity which has not resolved to Grade 2 or lower within 28 days and before starting asciminib treatment.
- Asymptomatic (Grade 2) pancreatitis if not resolved within 28 days
- Disease progression while on bosutinib treatment. The following events are considered disease progression:
 - Accelerated phase (AP) as defined by any of the following:
 - $\geq 15\%$ blasts in the peripheral blood or bone marrow aspirate, but $< 30\%$ blasts in both the peripheral blood and bone marrow aspirate.
 - $\geq 30\%$ blasts plus promyelocytes in peripheral blood or bone marrow aspirate.
 - $\geq 20\%$ basophils in the peripheral blood.
 - Thrombocytopenia ($< 100 \times 10^9/L$) that is unrelated to therapy.
 - Blast crisis (BC) as defined by any of the following:
 - $\geq 30\%$ blasts in peripheral blood or bone marrow aspirate
 - Appearance of extramedullary involvement other than hepatosplenomegaly proven by biopsy (i.e. chloroma).
- QTcF at time of switch > 480 msec or inability to determine QTc interval

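### Women who switch from bosutinib may start asciminib on a pregnancy test up to 42 days old (about 30 if a safety follow-up test applies), against 21 days at study entry, and pregnancy is not a listed bar to switching

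*Combined protocol and SAP*

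**What the plan says.** **At the switch**

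- The Table 7-5 footnote lets the bosutinib EOT test stand in for the switch-screening test: "Assessment does not need to be completed during the screening visit for patients in the treatment switch if already collected during the EOT". In Table 7-2 the serum pregnancy row shows "X (if not done at EOT") at S-Screening, is blank at S-Week 1 Day 1 and S-Week 2 Day 1, and resumes at S-Week 4.
- Section 7.1.2.2 sets the time limit: "The maximum allowed time frame for patients failing bosutinib to start treatment with asciminib is 42 days after bosutinib EOT". Table 7-6 gives the same window for the switch-screening ECG, Day -42 to -1.
- For repeated blood tests and ECGs, Section 7.1.2.2 adds: "The last test performed before start of asciminib dosing must meet the conditions for treatment switch as listed below". The conditions that prevent a switch are unresolved Grade 3 or 4 toxicity, unresolved Grade 2 pancreatitis, progression to accelerated phase or blast crisis, and "QTcF at time of switch > 480 msec or inability to determine QTc interval". Pregnancy is not among them.
- Section 4.1.1 says "Eligibility criteria for patients switching to asciminib are described in" Section 7.1. Switch eligibility is therefore set apart from the entry criteria in Sections 5.2 and 5.3.

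**At study entry**

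- Section 7.1.2: "All screening/baseline assessments (with the exception of Bone Marrow Aspirates) should occur within 21 days before Week 1 Day 1".
- Section 5.3, criterion 18, excludes "Pregnant or nursing (lactating) women".

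**Safety follow-up**

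The Table 7-1 pregnancy row appears to carry a mark under the safety follow-up visit, but Table 7-5 lists no such test. Section 6.3.3 requires adverse-event follow-up for 30 days after the last dose. No section says whether the safety follow-up visit takes place before a switch.

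**The concern.** Section 1.2.1.1 reports fetal malformations in the rat embryo-fetal study of asciminib, so a woman's pregnancy status at her first dose matters. The plan protects that moment at study entry with a screening window and an explicit exclusion. Neither is carried over to the switch, where the same drug is started.

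The Table 7-5 footnote is shared with hematology and chemistry. For those it removes a duplicate, because both are repeated at S-Week 1 Day 1. For pregnancy it can remove the only scheduled test between bosutinib EOT and S-Week 4. The last-test rule does not help, since it works only through the listed conditions. A site that follows the plan exactly could therefore dose a woman on a result older than entry would allow.

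**Working it through.** **1. The plan's own figure.** Six weeks x 7 = 42 days, as Section 7.1.2.2 states.

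**2. Age of the last result at first dose.** Take the EOT test as day 0, the EOT visit as the day of the last bosutinib dose (assumption), and the first asciminib dose as day s, with s from 0 to 42.

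- EOT test only: age = s, maximum 42 days.
- With a further test at day 30: age = s up to day 30 and s - 30 after it. The maximum is about 30 days, for a start just before that test. A start on day 42 gives 42 - 30 = 12 days.
- Study entry: maximum 21 days.
- Excess over entry: 42 - 21 = 21 days, or 30 - 21 = 9 days.

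**3. Worst-case gap to the next scheduled test.** Count Week 4 as 21 or 28 days after the first dose.

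| Situation | Age at first dose | Gap between tests |
|---|---|---|
| Randomized start | 21 | 21 + 21 to 28 = 42-49 |
| Switch, EOT test only | 42 | 42 + 21 to 28 = 63-70 |
| Switch, start just before a day-30 test | about 30 | 30 + 21 to 28 = 51-58 |
| Switch, start on day 42 after a day-30 test | 12 | 12 + 21 to 28 = 33-40 |

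Table 7-1 has no Day 1 pregnancy test at randomized start either, so the lack of one at S-Week 1 Day 1 is not itself the difference. The difference is the age limit and the listed exclusion.

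**4. How many women.** The Amendment 03-US.01 rationale gives 233 randomized, and 2:1 allocation gives 233/3 = 77.7 on bosutinib. The Amendment 3 rationale gives 4 potential switchers at 15-Oct-2018 and 86 randomized at 21-Nov-2018: 4/(86/3) = 4/28.7 = 14%. This is an early snapshot with mismatched dates and serves only as a low value. Assume 14-50% switch and 10-25% of switchers are of childbearing potential.

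- Low: 77.7 x 0.14 x 0.10 = 1.1 women.
- High: 77.7 x 0.50 x 0.25 = 9.7 women.

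**5. How many had still to switch at the latest amendment (05-Aug-2020).** Recruitment closed on 22-Oct-2019; adding 96 weeks (672 days) gives 24-Aug-2021. The window from Amendment 3 (14-Dec-2018) is 984 days, of which 384 remain: 384/984 = 39% if switches are evenly spread. Assume 10% if failures cluster early.

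- Remaining: 1.1 x 0.10 = 0.1 to 9.7 x 0.39 = 3.8 women.
- After an assumed 180-day approval delay: 204/984 = 21%, and 9.7 x 0.21 = at most about 2 women.

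**6. Expected conceptions by first dose.** Formula: women x annual rate x days/365. The rate of 1% per year is an assumption; criterion 19a mentions a failure rate below 1% without a time unit.

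- Full 42-day wait for all: 1.09 x 0.01 x 42/365 = 0.0013 to 9.7 x 0.01 x 42/365 = 0.011.
- Only the 21 days beyond the entry limit: half of that, 0.0006 to 0.0056.
- Among women still to switch, full 42 days: 0.11 x 0.01 x 42/365 = 0.0001 to 3.8 x 0.01 x 42/365 = 0.004.

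**The case against.** The strongest reply is that a switcher is not comparable with a patient at first screening. She has been tested about every four weeks up to Week 96. Section 7.2.2.5.3 expects highly effective contraception throughout the study, and criterion 19a carries it for one month beyond the last bosutinib dose. Unscheduled tests are available. Section 2.2 leaves the switch to the investigator's discretion and the patient's best interest. Section 7.1.6, which Section 4.1.1 applies to switchers, stops treatment for a pregnancy the patient wants to pursue. The 21-day entry window is a general screening rule, not a pregnancy-specific one. The IRT manual, which governs the switch checks, is not available here and may contain more.

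Most of this stands, and it is why the risk is very small. It does not close the gap. Section 7.1.6 needs a known pregnancy, depends on the patient's wish to continue it, and is worded as stopping treatment rather than barring a start. It schedules no test.

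A reader might infer that the plan puts no limit at all on the age of the test. The documents do not support that: the 42-day window caps it. What is missing is a shorter limit specific to this test. Nor do they support the reading that the plan knowingly allows dosing in pregnancy, given the contraception and discontinuation rules.

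**Conclusion.** The point holds as a modest safety improvement. For women of childbearing potential who switch, the result relied on may be 42 days old at first asciminib dose, or about 30 if a day-30 safety follow-up test precedes the switch, against 21 at entry. That is an excess of 9 to 21 days. The 30-day figure rests on the placement of a mark in Table 7-1, on a visit timed 30 days after the last dose, and on that visit being held for switchers; Table 7-5 does not confirm the test.

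No rule of the plan is broken, and no endpoint or efficacy analysis is affected. Expected conceptions by first dose are about 0.01 or fewer over the whole trial, given the assumed 1% annual rate, switch shares and childbearing shares. Only women who have not yet switched can benefit: about 0.1 to 4 at the date of the latest amendment, and at most about 2 after the assumed approval delay.

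**What to change.** - In Table 7-2, and in a pregnancy-specific footnote to Table 7-5, accept the EOT or S-Screening test only if taken within 21 days before the first asciminib dose, matching entry, or at most 4 weeks. Otherwise repeat it before dosing, at the latest at S-Week 1 Day 1; a urine test is enough. The present footnote should stay as it is for hematology and chemistry.
- Add a positive pregnancy test to the switch-preventing conditions in Section 7.1.2.2. The existing last-test rule then has something to act on.
- State whether the Table 7-1 safety follow-up visit, with its pregnancy test, applies to patients who switch.

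The cost is a short approved amendment and one extra hCG test, at an existing visit, for the few women whose result is too old. Urine kits would be needed at S-Week 1 Day 1, since the plan now provides for urine tests only after Week 96 or S-Week 96.
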